21.6 Appendix B: Questionnaire for Verifying Stroke-Free Status (QVSFS)

21.7 Appendix C: National Institutes of Health Stroke Scale (NIHSS)

21.8 Appendix D: Modified Rankin Scale (mRS)

21.9 Appendix E: Conscious Sedation Sub-Study Protocol

The Conscious Sedation Single Arm Sub-Study is designed to evaluate the safety and performance of the CLAAS System implantation procedure using conscious sedation.

A. Sub-Study Design

The Sub-Study is a prospective single arm trial evaluating a conscious sedation protocol. The Sub-Study will evaluate the safety and performance of the CLAAS System using conscious sedation in comparison with the device delivery safety and performance observed in the CLAAS arm of the RCT. The Sub-Study will be performed in accordance with all protocol requirements and all subjects will be evaluated for Primary Endpoint based on the product performance at the 45 days post procedure assessment. Enrollment in the Sub-Study will not commence until enrollment in the randomized cohort is complete, initial safety of the CLAAS system is confirmed by the DSMB and FDA approval of the Sub-Study has been granted through an IDE Supplement. All subjects enrolled in the conscious sedation single arm study will follow the same clinical protocol requirements and follow-up as the randomized subjects. The Sub-Study will be identified by an NCT that is separate from the RCT with Roll-in.

B. Eligibility Criteria

The Sub-Study will enroll subjects with the same inclusion and exclusion criteria utilized in the RCT study cohort. These enrollment criteria are provided in Section 8.5 of the RCT protocol.

C. Procedural Requirements

The Sub-Study will be performed using the same procedural and follow up assessments through 45 Days post procedure as outlined in the RCT phase of the study.

D. Screening/Baseline

The following tests and examinations must be performed prior to the index procedure to verify eligibility and to collect baseline study data. Assessments performed as part of standard medical care prior to study enrollment are valid sources of data for verifying study eligibility and collecting baseline study data, provided that the previously performed assessments comply with applicable protocol requirements.

- History and Physical (may be done per standard of **care up to 30 days prior to consent**). Physical assessment to include Height, Weight, Pulse and Blood Pressure.
 - Atrial fibrillation stroke risk assessment with the CHA₂DS₂-VASc scores
- Major bleeding risk assessment with the HAS-BLED score
- Neurological assessment (within 14 days of index procedure), to include:
 - Questionnaire for Verifying Stroke-Free Status (QVSFS)
 - NIH Stroke Scale (NIHSS); the NIHSS must be performed by a neurologist or NIHSS-certified research staff
 - Modified Rankin Scale (mRS) to establish the disability or dependence in the daily activities of people who have suffered a stroke or other causes of neurological disability at baseline; the mRS must be performed by a neurologist or research staff who have completed mRS training
 - Patients in whom an incident neurologic event is suspected on the basis of the QVSFS, NIHSS, or other signs or symptoms, will require a neurologic examination

and evaluation be performed by a neurologist or clinical designee (e.g., neurology fellow).

- Female patients of childbearing potential must have a pregnancy test (by site standard, either serum or urine) performed within 7 days of index procedure
- Laboratory testing per site standard practice as part of a catheterization procedure.
 Recording of the following Standard of Care labs shall be included as part of the study database: Serum Creatinine or GFR/eGFR; platelet count, HCT/HgB. Lab testing must be collected within 24 hours prior to the index procedure.
- A 12-lead electrocardiogram (ECG). An ECG performed within 30 days prior to the index procedure may be used as the baseline ECG, provided there have been no signs or symptoms of myocardial ischemia between the time of the ECG and the screening assessment (in which case the ECG should be performed within 24 hours prior to the index procedure).
- Brain imaging. For patients with a history of TIA/Stroke, a Brain Scan with MRI or CT is required within 6 months prior to consent. For all subjects with brain MRI scans performed in the 24-month period prior to consent, a repeat the MRI may be required by the Sponsor as a baseline reference, only if there is a suspected neuro event.
- Baseline TTE will be done to confirm subject eligibility and to serve as baseline for any
 potential adverse event assessments. Cardiac CT or MRI performed within 6 months prior
 to consent may be used in place of TTE only if all the exclusion criteria can be evaluated
 with this study. If not, a TTE is required at baseline. If a significant cardiac event occurs
 after the cardiac imaging which is potentially related to a change in cardiac status (e.g.,
 CHF decompensation), the TTE must be repeated prior to randomization. All cardiac CT
 images shall be uploaded to the image portal for review by the CT Imaging Core lab. See
 instructions for the CT imaging guidelines provided by the Core Lab in the Study Manual
 of Procedures.
- Medication assessment including the use of antiplatelet, anticoagulation, and antibiotic medication
- Relevant levels of INR.
- Eligibility Criteria Imaging will be performed to confirm subject eligibility (size, depth, presence of thrombus). Imaging must be performed within 14 days of index procedure.
- Patient must be maintained on anticoagulation during eligibility criteria imaging assessment until index procedure

E. Index Procedure

Trained Conformal representatives may be present during the CLAAS Implant procedure. Site personnel should contact Conformal to schedule the implant procedure with a proctor, as necessary.

E.1) Pre-Procedure Medical Therapy

Pre-procedure oral anticoagulation should be managed as per site protocol. Warfarin should be discontinued in accordance with site standard of care practices including INR levels on the day of the procedure.

The following loading doses should be administered prior to the index procedure:

- Aspirin
 - o ASA 81-100 mg (administered 1 day prior to procedure), or
 - ASA 325 mg (chewed 1 hour prior to procedure)

Antibiotic Prophylaxis

 Pre-procedure antibiotic for endocarditis prophylaxis should be administered prior to the procedure as per local standard of care.

E.2) Intraprocedural Medical Therapy

Intraprocedural anticoagulation with heparin should be administered per physician standard practice in accordance with published guidelines and local standards of care, with a goal of maintaining an activated clotting time (ACT) of 250-350 sec throughout the procedure. The highest and lowest intraprocedural ACT measurements shall be recorded in the CRF for all subjects.

Total heparin dose and prophylactic antibiotics administered, including the dose and timing, shall be recorded in the subject's medical record, and recorded on the eCRF.

E.3) Transseptal Puncture

Percutaneous femoral vein access and transseptal puncture should be performed per physician standard practice using a standard commercially available transseptal access system.

E.4) Study Imaging

Eligibility Criteria Imaging, procedural angiographic and ultrasound images will be uploaded using the image submission guidelines outlined in the Study Manual of Procedures.

At any time during the study, ultrasound imaging obtained during a repeat procedure or for diagnostic purposes should also be uploaded for analysis.

E.5) Implant Deployment

Implantation of the CLAAS device should be performed as per the IFU.

Procedural details will be captured as appropriate on the procedural worksheets and subsequently recorded on the eCRF. Any Adverse Events observed, or Device Deficiencies shall also be recorded in the EDC.

The procedure is considered complete once the last venous access sheath is removed or the subject has been discharged from the catheterization lab, whichever is first.

E.6) Anticoagulation/Antiplatelet Therapy Requirements - CLAAS

i) Post-Procedure

- If the final post procedural, post tether release imaging demonstrates adequate seal (residual leak ≤5 mm) and there is no evidence of thrombus, subjects *shall* receive DAPT (ASA 81-100 mg QD and clopidogrel* 75 mg QD) until 45 days post-procedure imaging.
- If the 45-day TEE demonstrates adequate closure: DAPT should be continued to 6 months; unless deemed unsafe by the subject's physician.

NOTE: A substitute P2Y12 inhibitor (i.e., prasugrel, ticagrelor) may be used as per managing physician's judgement. For patients who are known clopidogrel non-responder an alternative P2Y12 inhibitor should be used.

ii) Additional Considerations:

Inadequate seal: Subjects with inadequate seal (residual leak >5 mm) at the post-deployment imaging (or any subsequent imaging) should be evaluated for treatment with DOAC and ASA for 4-6 weeks followed by repeat TEE. If inadequate seal persists on TEE, antithrombotic therapy should be considered until seal is confirmed on the follow up imaging. Antithrombotic therapy should be individualized to the patient based on anatomic (size of leak) and clinical (risk of anticoagulation) considerations.

Device Related Thrombus: If thrombus is detected on the LA surface of the device on the post-procedure imaging (or any subsequent imaging), the subject should be evaluated for treatment with OAC and ASA for 4-6 weeks followed by repeat imaging. Antithrombotic therapy should be continued until confirmation of thrombus resolution has been documented on follow up imaging. Antithrombotic therapy should be individualized to the patient based on clinical (risk of anticoagulation) considerations

iii) Endocarditis Prophylaxis

Appropriate endocarditis prophylaxis is recommended for 6 months following device implantation. The decision to continue beyond 6 months is at the discretion of the principal investigator.

F. Pre-discharge Follow-up

Post-procedure assessment must occur during the index procedure hospitalization prior to hospital discharge or at 7 days post index procedure, whichever is sooner. The evaluation must include:

- Physical assessment (Weight, Pulse and Blood Pressure)
- TTE to evaluate for pericardial effusion
- Current concomitant medications documentation. If DAPT has been interrupted or terminated the stop date (and resumption date, if applicable) and the reason for interruption/termination should be recorded.
- A neurological assessment to evaluate neuro status of patient. If the assessment is indicative of a potential neurological deficit, further evaluation by a boardcertified neurologist or designee (e.g., neurology fellow) must be performed.
- Adverse event assessment

Prior to hospital discharge, research staff should review the follow-up requirements with the subject to ensure compliance with the subsequent follow-up assessment.

G. 7-day Follow-up + 2 Days (Telehealth Visit)

All subjects must undergo a follow-up assessment on day 7 to 9 post-procedure to enable timely documentation of safety endpoint events.

If the subject has not yet been discharged from the index procedure hospitalization at day 7 post-procedure, the 7-day follow-up may be conducted in-hospital, and no separate telehealth visit is necessary. In clinic visit will satisfy the telehealth visit, if appropriate.

The 7-day follow-up assessment must include:

- Questionnaire for Verifying Stroke Free Status (QVSFS). If any question is answered "Yes," a formal neurologic examination and evaluation must be performed by a board-certified neurologist or clinical designee (e.g., neurology fellow).
- Current concomitant medications documentation. If DAPT has been interrupted or terminated, the stop date (and resumption date, if applicable) and the reason for interruption/termination should be recorded.
- Adverse event assessment.

H. 45-day Follow-up ± 7 Days (Telehealth Visit and Imaging)

All subjects will complete an assessment at 45 days (±7 days) post-procedure with imaging (TEE) \and clinical evaluation through a minimum of a telehealth visit. The 45-day follow-up visit will include the following assessments:

- Questionnaire for Verifying Stroke Free Status (QVSFS) If any question is answered "Yes," a formal neurologic examination and evaluation must be performed by a board-certified neurologist or clinical designee (e.g., neurology fellow).
- A transesophageal echocardiogram (TEE) must be performed in all subjects who left the
 index procedure with an implanted device. Subjects in whom the TEE demonstrates
 significant residual leak (>5 mm), or thrombus must undergo a repeat TEE at 6 months.
 The TEE images will be required to be uploaded in accordance with Core Lab instructions
 provided in the Study Manual of Procedures.
- Current concomitant medications documentation.
- Adverse event assessment

Prior to concluding the visit, research staff should also review the follow-up requirements with the subject to help ensure study compliance.

NOTE: For subjects who did not leave the index procedure with an implanted device and/or did not have an implant attempt, the 45-day clinic follow-up is the final required follow-up assessment for this protocol, and the TEE imaging assessment is not required. The study exit form should be completed for these subjects at this time.

I. Primary Endpoints:

i) Primary Efficacy:

Successful implantation of the LAAO Device in the LAA with acceptable position, and complete closure or peri-device residual leak ≤5 mm in width on TEE, as evaluated by independent core lab at 45 days post-procedure and without in-hospital major procedure-related complications during hospitalization or at 7 days whichever is first.

ii) Primary Safety:

A composite of Major Procedure-related complications assessed through 45 days (listed below) as adjudicated by an independent Clinical Events Committee as related to either the study device or procedure.

Major Procedure-Related Complications includes any of the following specific events with the specific definitions outlined in Appendix A for each component:

- cardiac perforation,
- pericardial effusion requiring drainage,
- ischemic stroke,
- device embolization,
- major vascular complications

Statistical Considerations:

The sub-study is designed to demonstrate non-inferiority in CLAAS Implant success compared to the CLAAS arm of the RCT, based on the 45-day endpoint assessment. It is estimated that a total sample size of 130 subjects (including 6% attrition) is required to demonstrate non-inferiority. This estimated sample size will be verified and adjusted, if necessary, based on the observed rate of CLAAS Implant success rate in the RCT, prior to initiation of the sub-study.

J. Sample Size Determination

Subjects are enrolled in the Conscious Sedation Sub-Study when the subject has signed informed consent and has the procedure scheduled.

The Conscious Sedation Sub-Study will be analyzed by comparing subjects from the sub-study with subjects who receive the CLAAS Implant from the randomized cohort. The primary endpoint for the Sub-Study is Procedure Success at 45-days, defined as:

 successful implantation of the LAAO Device in the LAA with acceptable position, and complete closure or peri-device residual leak ≤5 mm in width on TEE, as evaluated by independent core lab [at 45 days post-procedure] and without inhospital major procedure-related complications during hospitalization or at 7 days whichever is first.

The goal of the Sub-Study will be to demonstrate non-inferiority between the two procedural techniques based on the Procedure Success at 45-day endpoint.

The endpoint will be assessed with the following non-inferiority hypothesis:

 H_0 : Pt - Pc \leq -0.10 H_A : Pt - Pc > -0.10

where Pt and Pc are the proportion of subjects with Procedure Success at 45-days in the treatment and control groups respectively and 0.10 represents the non-inferiority margin. The hypothesis will be evaluated using a one-sided 95% confidence interval for the difference in proportions based on a Farrington-Manning non-inferiority test. If the one-sided upper confidence bound for the difference is less than the non-inferiority margin, the objective will be met, and the treatment group will be non-inferior to the control group for the primary effectiveness endpoint.

It is anticipated that the Procedure Success for the CLAAS procedure with general anesthesia will be between 90-95%. As such, using a non-inferiority margin of 10%, and a one-sided 0.05 alpha level, a total of 130 subjects (including attrition of 6%, e.g., 122 evaluable subjects) in a conscious sedation sub study versus approximately 600 CLAAS subjects from the overall

randomized RCT would provide greater than 90% power. Calculations are based on a Farrington-Manning test of non-inferiority for binomial proportions.

The final statistical details will be confirmed as an amendment to the Statistical Analysis Plan prior to the enrollment of Sub-Study subjects.

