8.8.2 Conscious Sedation Population

The Conscious Sedation ITT subject is an individual who signs an ICF, has been assigned to the Conscious Sedation Cohort and has an implant procedure attempted. For this population, an implant procedure attempt (ITT established) is defined when the CLAAS Delivery Catheter is introduced into the body.

If an implant procedure is attempted without an implant placed, the subject must be followed through the Primary Safety and Efficacy Endpoints (at all visits including 7-days, 45-days, 6-months, 12-months, and 18-months) assessing only: QVSFS, AE Assessment, and Concomitant Medication Assessment. These assessments can be conducted via telehealth/phone call. These subjects will not be required to have subsequent protocol mandated imaging and will not be required to follow the medication requirements. If a subject in the Conscious Sedation Population experiences a suspected stroke or systemic embolism, that subject should be

brought in for an Unscheduled Visit (in-person clinic visit) for assessment per the Schedule of the Assessments matrix. After the 18-Month visit, these subjects will have completed all required study assessments.

Subjects who are scheduled for a conscious sedation procedure, but no longer meet eligibility criteria and do not have a procedure attempt (i.e., the CLAAS Delivery Catheter never entered the body) will be followed only through 45 days via telehealth/phone call visits. No protocol mandated imaging or medication therapy will be required. After the 45-Day visit, these subjects will have completed all required study assessments and will be classified as Screen Failures.

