Device Related Thrombus: If thrombus is detected on the LA surface of the device on the post-procedure TEE (or any subsequent TEE or Cardiac CT), the subject should be evaluated for treatment with OAC (Warfarin or DOAC), and ASA for 4-6 weeks followed by repeat imaging. Repeat imaging should be conducted per SOC or at the patient's next study visit. All additional SOC imaging (TEE or Cardiac CT) should be provided to the Sponsor for Core Lab Review. Antithrombotic therapy should be continued until confirmation of thrombus resolution has been documented on follow up imaging. Antithrombotic therapy should be individualized to the subject based on clinical (risk of anticoagulation) considerations.

9.6.3 Antiplatelet and Oral Anticoagulant Therapy Requirements (CONTROL):

Control subjects should be treated according to the marketed LAAO device manufacturer's Instructions for Use.

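### Appendix E ends follow-up at 45 days for sedation subjects left without an implant, while Section 8.8.2 follows attempted-but-not-implanted sedation subjects to 18 months; two other Appendix E instructions also need reconciling

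*Protocol*

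**What the plan says.** **End of follow-up.** Section 8.8.2 (Conscious Sedation Population) states: "If an implant procedure is attempted without an implant placed, the subject must be followed through the Primary Safety and Efficacy Endpoints". It lists the 7-day, 45-day, 6-, 12- and 18-month visits and closes with "After the 18-Month visit, these subjects will have completed all required study assessments". Only subjects with no attempt stop at 45 days there. The note in Appendix E part H covers subjects who left without a device, had no attempt, or both. For all of them "the 45-day clinic follow-up is the final required follow-up assessment for this protocol", and the exit form is completed then. Part A of the same appendix says that every sub-study subject follows the randomised subjects' protocol requirements and follow-up. Part C speaks of assessments through 45 days.

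**Anticoagulation before the procedure.** Part D: "Patient must be maintained on anticoagulation during eligibility criteria imaging assessment until index procedure". Part E.1 leaves oral anticoagulation to site protocol and adds: "Warfarin should be discontinued in accordance with site standard of care practices including INR levels on the day of the procedure".

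**Re-imaging.** For device-related thrombus, part E.6 says that the subject "should be evaluated for treatment with OAC and ASA for 4-6 weeks followed by repeat imaging". It gives a parallel instruction, with repeat TEE, for a leak above 5 mm. Part H says that subjects whose 45-day TEE shows a leak above 5 mm "or thrombus must undergo a repeat TEE at 6 months".

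**The concern.** The first pair of rules conflicts directly for one identifiable group: sedation subjects in whom the delivery catheter entered the body but no implant was placed. A site using the appendix would close the record at 45 days; a site using the main protocol would keep telephoning to 18 months. Randomised subjects with an attempt and no implant are followed to 18 months under Section 8.8.4, so part H also breaks the appendix's own promise of equal follow-up. At stake is the recording of strokes, emboli and other adverse events after day 45 in these subjects, and whether sites do the same thing.

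The other two pairs leave sites with differing instructions on anticoagulation before the procedure and on the timing of repeat imaging after a thrombus or large leak.

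**Working it through.** **1. The plan's own figure.** Appendix E part J gives 122 evaluable subjects, 6% attrition, about 600 RCT comparators, a margin of 0.10, one-sided alpha of 0.05 and success of 90–95%.

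- Inflation: 122 / (1 − 0.06) = 129.8, so 130. Reproduced.
- Farrington-Manning power = Φ[(0.10 − 1.645 × SE0) / SE1]. At a true rate of 0.90 in both groups, the restricted null rates are 0.8098 and 0.9098.
  - SE0 = √(0.8098 × 0.1902/122 + 0.9098 × 0.0902/600) = 0.0374
  - SE1 = √(0.90 × 0.10 × (1/122 + 1/600)) = 0.0298
  - Power = 90.2%
- At 0.95 the same calculation gives 98.3%. The claim of more than 90% is reproduced.

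Both sub-study primary endpoints are read by day 45, and both follow-up rules reach day 45. Neither number changes.

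**2. Follow-up rules side by side.**

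| Sedation subject | Section 8.8.2 | Appendix E part H |
|---|---|---|
| No attempt | 45 days | 45 days |
| Attempt, no implant | 18 months | 45 days, then exit |

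Only the second row conflicts. The schedule of assessments puts 18 months at day 545, so the difference is 545 − 45 = 500 days.

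**3. How many subjects.** Sections 6.3 and 6.4 give the feasibility results.

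- Second phase of the US study: 41 of 42 implanted, a failure rate of 1/42. 130 × 1/42 = 3.1.
- Adding the Prague study, done under conscious sedation with success in 15 + 4 = 19 subjects: 1/(42 + 19) = 1/61. 130 × 1/61 = 2.1.

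The range is 2 to 3 subjects. It excludes the first US phase, whose four failures came before the Large device was available.

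**4. Anticoagulation.** Part D is a requirement that runs up to the procedure. Part E.1 defers to the site and expects warfarin to stop according to site practice. Both are met only where site practice is uninterrupted therapy.

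**5. Re-imaging after a finding at the 45-day TEE.** The visit window is day 38 to 52. Assume treatment starts on the day of the finding.

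- Part E.6: 38 + 28 = 66 at the earliest and 52 + 42 = 94 at the latest, so day 66–94.
- Part H: 6 months with the main schedule's ±30 days is day 150–210.

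The windows do not overlap; they lie between 150 − 94 = 56 and 210 − 66 = 144 days apart. A site could perform both scans, and nothing says whether it must.

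**The case against.** **Does 8.8.2 really mean 18 months?** It speaks of the primary endpoints, and the sub-study's own primary endpoints fall at 45 days; part C also runs only to 45 days. This does not rescue the text, because 8.8.2 names the visits to 18 months and ends required assessments there. Nor can the note in part H be confined to subjects with no attempt, since it expressly includes those who left without a device.

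**Does it matter to the comparison?** A reader might infer that the appendix's safety rules are unworkable or that the sub-study result is compromised. The documents do not support that. The primary endpoints are complete by day 45, and part J names RCT subjects who receive the CLAAS implant as the comparator. This part of the objection stands.

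**Are the other two pairs contradictions?** The imaging pair is not strictly one, since both scans can be done. The anticoagulation pair is compatible at some sites. A reader might also infer from Section 9.6.2 that thrombus re-imaging is tied to a visit with no scheduled imaging. The sentence reads "Repeat imaging should be conducted per SOC or at the patient's next study visit", so standard-of-care imaging is an express alternative, and that inference fails.

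**Could more subjects be affected?** Pooling both US phases gives 5/64, or 130 × 5/64 = 10.2 subjects. Four of those five failures were in appendages too large for the Regular device before the Large one was available, so 10 is not a fair projection.

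**Is there time?** Yes. Sub-study enrolment waits for RCT enrolment to finish and for approval of an IDE supplement. This makes correction easy; it does not make the texts agree.

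**Conclusion.** The end-of-follow-up rules for sedation subjects with an attempt but no implant contradict each other in current text. Under Appendix E part H, about 2 to 3 of 130 subjects would leave roughly 500 days before Section 8.8.2 allows. The count assumes that feasibility failure rates after the first US phase carry over. It rests on a single failure, so it is an order of magnitude only. The 45-day endpoints, the sample size and the stated power stand; the loss is later safety capture and uniform conduct across sites.

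The anticoagulation conflict between parts D and E.1 is real but narrower. The relation between the E.6 and H imaging instructions is unstated rather than contradictory. No view is taken here on which clinical rule is right.

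**What to change.** Before the sub-study opens:

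1. Reconcile Section 8.8.2 and Appendix E parts A and H into one end-of-follow-up rule for attempted-but-not-implanted sedation subjects. Bring part C into line with it.
2. Reconcile Appendix E part D with E.1 on anticoagulation before the procedure.
3. State whether the 6-month TEE in part H replaces or adds to the repeat imaging in E.6.

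The sponsor and investigators should set the clinical content of each. The cost is an edit to the appendix and possibly Section 8.8.2. It needs its own amendment, because the update promised at the end of Appendix E is to the statistical analysis plan, not to the appendix. If the longer follow-up rule is kept, the added burden is telephone or telehealth contacts to 18 months for a few subjects.
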